9.4 Routine Electrocardiograms during the long-term follow-up study

Routine ECGs are only collected during the long-term follow-up study before protocol amendment 4 was approved. ECG parameters include QTc interval, QT interval, QTc interval (Fridericia), PR interval, RR interval, and QRS duration. The dose monitoring ECGs will be excluded from routine ECG summaries.

ECG data will be summarized by presenting descriptive statistics for baseline, post-baseline, and change from baseline values (relative to the first dose of fingolimod during the long-term follow-up study) by parameter and nominal visit. Incidence of abnormal ECGs will be presented by nominal visit.

A listing of ECG data for patients with abnormal findings will be provided for safety set.

9.5 Dose monitoring administration

First-dose monitoring should be done on any patient who enrolls into this long-term follow-up study part I from any blinded study which has comparator treatment arms (placebo or active comparator, e.g. study CFTY720D2309) or enrolls from the comparator arm of an open-label controlled study or for any patient who has been off fingolimod treatment for the following durations:

- The treatment lasted for 14 days or less and was interrupted for 1 day or more, or
- The treatment lasted for more than 14 days and less than 29 days and was interrupted for more than 7 consecutive days, or
- The treatment lasted for 4 weeks or more and was interrupted for more than 14 consecutive days.

Patients requiring first dose monitoring should receive the first dose of fingolimod at the study center at a time which will allow for the required 6-hour post-dose monitoring to occur as well as to allow for additional time for extended monitoring, if necessary. The patient may be discharged if specific discharge criteria (refer to Protocol Appendix 4) are met. Hourly monitoring will be extended until findings have resolved if the discharge criteria are not met, and should pharmacologic intervention be required during first-dose observation, overnight monitoring in a medical facility should be instituted and the first-dose monitoring procedures should be repeated upon the 2nd dose.

A dose administration monitoring summary will be provided for the safety set for first/second/restart of fingolimod dose during the long-term follow-up study part I, and will include yes or no categorical summaries for the following: discharged at 6 hours, required extended monitoring after 6 hours, discharged but returned for monitoring, hospitalization, required Day 2 monitoring in the clinic (only recorded for first dose monitoring), study drug permanently discontinued, had symptomatic and/or treated bradycardia, and SAEs reported. The denominator for first/second dose monitoring data is based on the number of patients with assessment done; the denominator for restart monitoring data is based on the number of restarts.

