## **Appendix 4: Guidance for Monitoring of patients taking their first dose of the study drug**

Initiation of fingolimod treatment results in a transient decrease in heart rate. After the first dose, the heart rate decrease starts within an hour and the Day 1 decline is maximal within 6 hours. With continued dosing, heart rate returns to baseline within one month of chronic treatment. In patients receiving fingolimod 0.5 mg this decrease in heart rate, as measured by pulse, averages approximately 8 beats per minute (bpm). Heart rates below 40 bpm were rarely observed. Patients who experienced bradycardia were generally asymptomatic but some patients experienced mild to moderate symptoms.

Initiation of fingolimod treatment has been associated with AV conduction delays, usually as first-degree atrio-ventricular blocks. Second-degree AV blocks, usually Mobitz type I (Wenckebach) have been observed in less than 0.5% of patients receiving Gilenya 0.5 mg in clinical trials. The conduction abnormalities typically were transient, asymptomatic, usually did not require treatment and resolved within the first 24-hours on treatment. Isolated cases of transient, spontaneously resolving complete AV block have been reported during post-marketing use of fingolimod 0.5 mg.

Therefore, guidance on the monitoring of patients taking their first dose or re-initiating treatment after interruption of treatment is provided.

The on-site first-dose administration monitoring is mandatory for the following patients:

- At the Baseline visit, in all patients enrolling into this trial from blinded controlled trials and patients from open-label controlled trials coming off the comparator arm.
- Patients who are off fingolimod treatment for the following durations:
- The treatment lasted for 14 days or less and was interrupted for 1 day or more, or
- The treatment lasted for more than 14 days and less than 29 days and was interrupted for more than 7 consecutive days, or
- The treatment lasted for 4 weeks or more and was interrupted for more than 14 consecutive days.

If applicable, the independent first-dose monitoring physician is responsible for monitoring following the 1st intake of the study drug and management of bradycardia symptoms should these occur. He/she must review vital signs during 6-hour monitoring, post-dose ECG and assess discharge criteria at 6 hours post-dose.

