Upon signing the informed consent, patients will be transferred into this study from one of the ongoing fingolimod core/extension studies (CFTY720D2201/E1, CFTY720D2301/E1, CFTY720D2302/E1, CFTY720D2309/E1, etc.), as well as from designated ongoing or newly starting fingolimod MS studies. In addition, phase II/III patients that have already completed CFTY720D2399, CFTY720D2309/E1, or one of the phase II/III extension studies will be able to enroll into this study. Patients will be provided with fingolimod 0.5 mg/day once a day treatment until study completion.

Patients who participated in double-blind studies and are directly entering this study will remain blinded to the identity of the treatment in the previous study. In order to maintain the blind, the monitoring immediately after the first dose of study drug will be performed by a blinded first-dose administrator.

This study has two parts:

Part One will collect long-term safety, tolerability, efficacy, and health outcomes data through approximately 30-Jun-2016. Part Two will collect limited safety data until approximately 30-Jun-2018 from a subset of patients participating in Part One and other

eligible patients from ongoing fingolimod trials (e.g., CFTY720D2312). Eligibility for Part Two is defined as prior fingolimod study patients who are unable to obtain fingolimod outside a clinical trial.

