2.1 Allocated treatment

All patients during the long-term follow-up study are treated with fingolimod 0.5 mg per day. The summaries for data collected during the long-term follow-up study part I will only present one total group (the same as fingolimod any dose). However, patients may have been assigned a different dose (5 mg, 1.25 mg) in their initial fingolimod trial. The summaries for data collected from first dose of fingolimod among all studies will be presented by highest assigned dose of fingolimod; only two groups will be presented: fingolimod 0.5 mg and fingolimod any dose.

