9.5.1 Vital signs

During the long-term follow-up study part I, hourly vital signs, including sitting pulse rate and blood pressure will be monitored before the first dose of fingolimod and every hour for at least six-hours thereafter.

Hourly dose monitoring of vital signs will be summarized separately and will not be included in the by-visit summaries of routine vital signs. Descriptive statistics of pre-dose, post-dose, and change from pre-dose values will be summarized by parameter and time point for first dose monitoring, second dose monitoring, and dose monitoring after study drug restart. Summaries will be based on the safety set and include dose monitoring data during the long-term follow-up study part I only.

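### The Part I first-dose monitoring tables can mix first-ever fingolimod doses with doses in patients already on fingolimod, which moves the summaries toward no effect

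*SAP*

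**What the plan says.** **Who is monitored.** Part I SAP section 9.5 calls for first-dose monitoring of "any patient who enrolls into this long-term follow-up study part I from any blinded study which has comparator treatment arms", of entrants from the comparator arm of an open-label controlled study, and of anyone with a qualifying interruption. Protocol Appendix 4 has the same rule: monitoring is mandatory at Baseline "in all patients enrolling into this trial from blinded controlled trials and patients from open-label controlled trials coming off the comparator arm". In blinded studies the arm does not matter. In open-label studies only the comparator arm is monitored at entry.

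**Link to the earlier blind.** The SAP Overview says: "In order to maintain the blind, the monitoring immediately after the first dose of study drug will be performed by a blinded first-dose administrator".

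**How the data are shown.** Section 2.1: "The summaries for data collected during the long-term follow-up study part I will only present one total group". Section 9.5 gives the denominator: "The denominator for first/second dose monitoring data is based on the number of patients with assessment done". Restarts have their own denominator, the number of restarts. Under section 9.5.1 the hourly vital signs "will be summarized by parameter and time point for first dose monitoring, second dose monitoring, and dose monitoring after study drug restart". Section 9.5.2 splits the ECG statistics only into first and second dose monitoring. The subgroups in section 2.5.1 are defined for adverse event analysis only. Nothing in 9.5 to 9.5.2 separates patients by prior fingolimod exposure.

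**The concern.** A patient who enters directly from the fingolimod arm of a blinded study takes a first dose in this study that is not a first exposure. Appendix 4 ties the heart-rate fall and the conduction delays to starting treatment. Averaging such patients with true initiators gives a result that describes neither group.

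First-dose cardiac effects are a named safety interest (Protocol sections 1.1 and 6.5.9). Dose-monitoring values are also kept out of the routine vital sign and ECG summaries (Part I SAP sections 9.3 and 9.4). The tables under 9.5 are therefore the planned summaries of measured hourly pulse, blood pressure and 6-hour ECG change. A reader who takes first dose to mean first exposure could conclude that the effect here was smaller than previously reported, when the difference came only from the mix of entrants.

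**Working it through.** The plan gives no figure for this point, so there is none to reproduce. The study is descriptive, and no sample size, power or test is involved.

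**Step 1: can the group be mixed?** Yes. Appendix 4 and SAP 9.5 include all arms of blinded comparator studies, and the SAP gives D2309 as an example. D2312 and D2402 patients appear in listings only (SAP section 2), so any mixing in the tables comes from other blinded feeder studies.

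**Step 2: do the groups differ?** By the protocol's account, yes. Appendix 4 gives an average fall of about 8 bpm on starting 0.5 mg, and says that with continued dosing "heart rate returns to baseline within one month of chronic treatment". It reports second-degree AV block in fewer than 0.5% of patients, as an effect of initiation.

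**Step 3: size.** Inputs:

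- E1, mean fall at true initiation: 8 bpm (Appendix 4).
- E0, mean fall after the monitored dose in a patient already on fingolimod: not given. Assumed 0, with 1 bpm as a sensitivity value.
- c, share of the first-dose group already on fingolimod without a qualifying gap: not given. Shown at 10%, 1/3 and 1/2.

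Pooled fall = (1 − c) × E1 + c × E0.

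| c | E0 = 0 | E0 = 1 bpm |
|---|---|---|
| 10% | 0.9 × 8 = 7.2 | 7.2 + 0.1 = 7.3 |
| 1/3 | 0.667 × 8 = 5.3 | 5.33 + 0.33 = 5.7 |
| 1/2 | 0.5 × 8 = 4.0 | 4.0 + 0.5 = 4.5 |

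An event that occurs only at true initiation has its percentage multiplied by (1 − c). The 0.5% ceiling for second-degree AV block would become 0.45%, 0.33% and 0.25%. The number of events does not change.

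**Step 4: direction.** Whenever c is above 0 and E0 is smaller than E1, the pooled figure lies nearer to no effect. Blood pressure and ECG intervals follow the same formula as far as they change at initiation. The documents give a mean change only for heart rate.

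**Step 5: can the groups be separated?** Yes. SAP section 2.3.2 derives study day both from the first fingolimod dose across all studies and from the first dose in this study. Section 5.3 already summarises fingolimod exposure before the first dose in this study.

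**The case against.** The strongest defence is that the tables do not set out to estimate a first-exposure effect. Section 9.5 summarises first, second and restart doses taken during Part I. Many of its items, such as discharge at 6 hours or return for monitoring, are conduct outcomes for which everyone assessed is the natural denominator. The objective is long-term safety, no inference is planned, and Protocol 6.5.9 treats the cardiac effects as already known. This stands as a reason to keep the pooled column. It does not help a reader who wants the measured change at initiation, because 9.5.1 and 9.5.2 report pre-dose to post-dose changes under a first-dose label.

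Four further objections limit the point, and all four stand.

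- **The size is unknown.** The share could be small. The usual route in the SAP Overview is core study, then extension, then this study, and sections 8.2.1 and 8.2.3 describe control patients switching to fingolimod in the extension.
- **Zero is an assumption.** Appendix 4 says that heart rate returns to baseline. It does not give the change over six hours of observation in a treated patient. The 8 bpm is the Day 1 fall, not a prediction for any one hourly row.
- **Other outputs exist.** A reader might infer that these tables are the study's only evidence on first-dose effects. They are not. Adverse event rates run from the first fingolimod dose across all studies (9.1.2.2), and patients with abnormal monitoring ECGs are listed (9.5.2).
- **The reason for monitoring is not stated.** A reader might infer that continuing patients are monitored only to protect the blind. The open-label rule makes that plausible, but the documents link the blind only to the blinded administrator. A former fingolimod-arm patient with a qualifying gap would be monitored anyway.

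**Conclusion.** The point holds as a presentation problem with a known direction and an unknown size. The stated monitoring rule, single group and denominator allow patients already on fingolimod into the first-dose summaries, and no planned split takes them out. Given Appendix 4, their presence makes the summarised first-dose changes and percentages look smaller than they are in true initiators.

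The illustrative range, from 7.2 bpm at a 10% share to 4.0 bpm at one half, rests on two assumptions: the share itself, and no change in continuing patients. The documents do not support a claim that the dilution is large. They also do not support a claim that the primary safety results are biased: adverse event incidence rates, event counts and listings stay as they are, and no test is affected. The pooled column need not be dropped.

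**What to change.** In Part I SAP sections 9.5, 9.5.1 and 9.5.2, keep the pooled column, labelled as an operational summary, and add two columns to each first-dose monitoring table:

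- **First-ever dose:** the date of first fingolimod dose across all studies equals the first dose date in this study.
- **Previously treated:** the date of first fingolimod dose is earlier.

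Where prior-study dosing dates allow, show separately the previously treated patients who had a qualifying Appendix 4 gap at entry, because an initiation-type effect may return in them. State whether such entrants count as first dose or restart, since section 9.5 does not say. Base any statement on first-dose cardiac effects on the first-ever-dose column.

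The two-way split uses dates that the SAP already derives and needs no new data. The gap split takes more work, because it needs interruption dates from the feeder studies, and gaps may include commercial fingolimod (Protocol 6.2). The other cost is fewer patients per column. Part 2 SAP section 9.4 has the same denominator, but there the ECGs are only listed, so the change matters mainly for Part I. No monitoring or treatment rule changes.

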9.5.1 Vital signs

During the long-term follow-up study part I, hourly vital signs, including sitting pulse rate and blood pressure will be monitored before the first dose of fingolimod and every hour for at least six-hours thereafter.

Hourly dose monitoring of vital signs will be summarized separately and will not be included in the by-visit summaries of routine vital signs. Descriptive statistics of pre-dose, post-dose, and change from pre-dose values will be summarized by parameter and time point for first dose monitoring, second dose monitoring, and dose monitoring after study drug restart. Summaries will be based on the safety set and include dose monitoring data during the long-term follow-up study part I only.

9.5.2 Electrocardiograms

During the long-term follow-up study part I, all patients requiring first dose monitoring will have an electrocardiogram (ECG) performed prior to dosing and at the end of the 6-hour monitoring period.

The hourly dose monitoring ECG will be summarized. Descriptive statistics of pre-dose, post-6 hour dose, and change from pre-dose values will be summarized by parameter and time point for first dose monitoring and second dose monitoring. The incidence of patients with abnormal ECG monitoring records will be summarized by time point, finding type, and finding.

Patients with abnormal dose monitoring ECG findings records will be listed. Summaries and listing will be based on the safety set and include dose monitoring data during the long-term follow-up study part I only.

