### **6.5.6 Electrocardiogram (ECG)**

First dose ECGs will be collected as described in [Table 6-1](#) and [6-2](#). Two ECGs are required for first-dose monitoring and will be performed for those patients rolling into this trial from a blinded trial, a trial which has a comparator treatment arm, as well as for any patient who has been off fingolimod treatment for the duration outlined in [Appendix 4](#).

The first ECG will be performed prior to the study drug administration; the second ECG will be performed approximately 6-hours post-first dose, prior to the patient being discharged. If study drug treatment is interrupted and treatment re-initiation meets the requirement for observation (See [Appendix 4](#)), the above procedures will be repeated.

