#### **9.4.1.4 Electrocardiograms**

Analysis will be performed for first dose ECGs during the long-term follow up study based on the safety set.

Summary statistics for ECG parameters (including pre-dose ECG for patients who have this evaluation done) will be summarized by time point and visit. Incidence of abnormal ECGs will be presented.

A listing of ECG data for patients with abnormal findings will be provided.

[REDACTED]

The same analysis including data collected during the Study Part Two will be conducted for the subgroup of patients who entered Study Part Two.

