9.4.2 Electrocardiograms

During the study part 2, all patients requiring first dose monitoring will have an electrocardiogram (ECG) performed prior to dosing and at the end of the 6-hour monitoring period.

ECG dose monitoring records will be listed for the safety set.

10 Sample size and power considerations

Given that this is a long-term follow-up study with primary descriptive purpose, no formal sample size calculation will be used to determine enrollment in this study. The sample size is defined by the number of patients coming from study part 1 and ongoing fingolimod trials.

Appendices

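### Dose-monitoring ECGs at treatment restart have no change table in SAP Part I, and SAP Part 2 only lists dose-monitoring ECGs although the protocol plans summaries

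*SAP*

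**What the plan says.** **Collection.** Protocol 6.5.6 requires an ECG before dosing and another at about 6 hours for first-dose monitoring. It then provides for restarts: "If study drug treatment is interrupted and treatment re-initiation meets the requirement for observation", both procedures are repeated. Footnote 8 of Table 6-1 and footnote 8 of Table 6-2 both include patients returning after an interruption of the lengths given in Appendix 4. Protocol 8.3 says that ECGs are done locally and the outcomes entered in the database.

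**SAP Part I.** The categorical dose-monitoring summary in 9.5 is given "for first/second/restart of fingolimod dose during the long-term follow-up study part I", with the number of restarts as the restart denominator. Hourly vital signs in 9.5.1 are summarised "for first dose monitoring, second dose monitoring, and dose monitoring after study drug restart". The ECG statistics in 9.5.2 "will be summarized by parameter and time point for first dose monitoring and second dose monitoring". The same section continues: "The incidence of patients with abnormal ECG monitoring records will be summarized by time point, finding type, and finding". It also plans a listing of abnormal records. The routine ECG summaries in 9.4 exclude dose-monitoring ECGs.

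**Part Two.** Protocol 9.4.1.4 plans ECG summary statistics, incidence of abnormal ECGs and a listing of patients with abnormal findings. It closes: "The same analysis including data collected during the Study Part Two will be conducted for the subgroup of patients who entered Study Part Two". SAP Part 2 9.4.2 says only: "ECG dose monitoring records will be listed for the safety set".

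**The concern.** A slowing of heart rate and delayed AV conduction at initiation are documented effects of fingolimod (protocol 1.1 and Appendix 4). Appendix 4 also explains that the 6-hour ECG is there to detect conduction events that cause no symptoms. Restarts are the occasions on which patients already in the study face that exposure again. The protocol itself gives rise to some of them, through interruptions for confirmed low lymphocyte counts (5.5.5), varicella vaccination (6.5.4.2) and pregnancy (6.5.8).

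If 9.5.2 is programmed as written, the report will show the change in pulse and blood pressure after restart but not the change in PR or QTc. In Part 2, an analysis that the protocol assigns to the primary safety variables would be replaced by a listing, with nothing to tell a reader that the plan had changed.

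**Working it through.** No arithmetic applies. The study is descriptive, with no hypothesis test and no calculated sample size (protocol 9.4.1 and 9.6). The check compares which planned output covers which ECG records.

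**Step 1. SAP Part I, coverage by dose type**

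| Output | First dose | Second dose | Restart |
|---|---|---|---|
| Categorical monitoring outcomes (9.5) | yes | yes | yes, own denominator |
| Vital signs: pre-dose, post-dose, change (9.5.1) | yes | yes | yes |
| ECG: pre-dose, 6-hour, change (9.5.2) | yes | yes | not named |
| ECG abnormality incidence and listing (9.5.2) | dose type not restricted | dose type not restricted | dose type not restricted |
| Routine ECG tables (9.4) | excluded | excluded | excluded |

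Only the ECG change table names two dose types where its neighbours name three. Because 9.4 excludes these ECGs, no other Part I table picks up the restart values.

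**Step 2. Part Two, protocol 9.4.1.4 against SAP Part 2 9.4.2**

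| Output | Protocol | SAP Part 2 |
|---|---|---|
| Summary statistics by time point and visit | planned | absent |
| Incidence of abnormal ECGs | planned | absent |
| Listing | abnormal findings | all dose-monitoring records |

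One of the three planned outputs remains, in a wider form.

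**Step 3. Does the protocol really intend the summaries for Part Two?** Some text just before the closing sentence of 9.4.1.4 is blacked out, so I looked for support elsewhere.

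- The AE and vital-sign sections (9.4.1.1 and 9.4.1.3) close with the same sentence, and there it refers to the analyses set out above it.
- The synopsis applies its analyses to both parts unless it says otherwise. It plans ECG summaries and abnormal ECGs by type without a limit, but marks the liver-test table as Part One only.
- Where no Part Two analysis is wanted, the protocol says so: laboratory (9.4.1.2), ophthalmic (9.4.1.5), pulmonary function (9.4.1.6) and skin (9.4.1.7). ECG has no such exemption.
- Table 6-2 marks the first-dose ECG for entry in the clinical database, and section 9 of SAP Part 2 names dose-monitoring ECGs among the safety assessments.

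**Step 4. Is Part 2 consistent within itself?** SAP Part 2 9.4 and 9.4.1 summarise monitoring outcomes and hourly vital signs, restarts included. Only the ECGs from the same monitoring sessions are reduced to a listing.

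**The case against.** **Restarts may already count as first-dose monitoring.** SAP Part I 9.5 extends first-dose monitoring to restarts: it is done "for any patient who has been off fingolimod treatment for the following durations". Footnote 8 of Table 6-1 likewise treats ECGs at re-initiation as first-dose ECGs, and protocol 9.4.1.4 asks for no separate restart stratum. On that reading 9.5.2 pools them. This shows an ambiguity, but it does not close the gap: the outputs in 9.5 and 9.5.1 separate restart from first dose, so a programmer following the same data structure would leave restarts out of the ECG table. If pooling was meant, it would mix initial starts with restarts, unlike the adjacent tables. The text needs clarifying either way.

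**Restart cardiac safety is largely visible elsewhere.** This stands. A reader might infer that Part I cannot report AV block after a restart. The documents do not support that. The abnormality incidence and listing in 9.5.2 carry no limit by dose type. The 9.5 summary tabulates extended monitoring, hospitalisation, symptomatic or treated bradycardia, discontinuation and SAEs at restart. Under Appendix 4, second- or third-degree block, or a QTc of 500 ms or more, at 6 hours fails the discharge criteria, so such cases should also appear there under extended monitoring.

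**Part 2 numbers are probably small.** This also stands. Part One patients who continue treatment enter at Visit 201A, which has no first-dose ECG (Table 6-2). Patients from D2312 and D2402 are left out of every Part 2 summary (SAP Part 2, section 2). What remains is mainly restarts, and the listing loses no record. That could justify listing-only reporting, but SAP Part 2 does not say so.

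**Conclusion.** The point holds in two limited parts. In Part I, ECG values and changes at restart have no named table, and restart abnormalities have no stratum of their own. In Part 2, the protocol's ECG summary statistics and abnormality incidence are replaced by a listing without a stated reason.

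The size can be given only as coverage: one missing dose type in one Part I table, one missing stratum in another, and two of three planned outputs absent in Part 2. A reader might want to scale this from the roughly 4,150 enrolled patients. The documents do not allow it: they give neither a restart rate nor a standard deviation for ECG change, and that enrolment figure describes the whole study, not Part 2. Nor do they show that restarts supply most of the dose-monitoring ECGs in Part I, since patients coming from blinded controlled trials also have them.

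No test or inferential conclusion is affected. The conclusion for Part 2 assumes that the blacked-out text in protocol 9.4.1.4 does not exempt ECGs; step 3 makes an exemption unlikely.

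**What to change.** **SAP Part I 9.5.2.** Add dose monitoring after study drug restart to the descriptive and change table, in the same terms as 9.5.1. In the abnormality table, show restart as a separate stratum with the number of restarts as denominator, as in 9.5. Because a patient can restart more than once, count restarts with an abnormal record in the numerator of that stratum.

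**SAP Part 2 9.4.2.** Add the protocol 9.4.1.4 summary (pre-dose, 6-hour and change, and abnormal findings by type) for the dose-monitoring ECGs available, which will mainly be restarts. Keep the listing. If there are too few to summarise, record listing-only as a justified change from protocol 9.4.1.4.

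**Cost.** SAP wording, extra panels in the existing Part I tables, and short Part 2 ECG tables built on the same layout. No new data are needed.
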